**CONFIDENTIAL AND PROPRIETARY**

- 
- Data Collection Stage – data entry and management are ongoing leveraging the electronic data capture system and secured database.
  - Statistical Processing and Data Analysis – is expected to take 1-3 months from the data entry of the last patient visit or the last patient enrolled.

## 4.5 Procedures

The ECG Belt study methodology is composed of:

- 1 scheduled clinic visits (baseline)
- 1-week follow-up monitoring period for adverse events (phone call).

### Visit 1 – Baseline

The following activities will be completed at Visit 1 (Baseline):

- Subjects will be screened to ensure they meet ALL the inclusion criteria and NONE of the exclusion criteria.
- Subjects will sign an Informed Consent form before any of the study related procedures are performed.
- Sequentially ordered subject identification number will be assigned for the specific site.
- Demographic
- Medical history
- Concomitant medication specifically ACE/ARB, beta blockers, diuretics, and anti-arrhythmics use
- Relevant co-morbidities will be recorded
- NYHA Functional Classification
- Collection of device characteristics and implanted system description.
- ECG Belt Research System Procedure\*
  - LBBP

**CONFIDENTIAL AND PROPRIETARY**

- 
- Native conduction
  - RV pacing if available
  - Bipolar LBBAP
  - Unipolar LBBAP – nonselective and selective (different outputs)
  - Fusion pacing with native conduction at different AV delays
  - HOT-CRT
    - Native conduction
    - HBP / LBBAP
    - HOT-CRT
    - AV delay optimization.
  - Medtronic Device (pacemaker/ICD) based Holter recording during the ECG belt recording\*\*
  - 12-lead ECG (Rhythm Strips)
  - Adverse Events related to ECG Belt

\*The use of the ECG Belt Research System may add approximately 40 minutes of time to follow-up visits for testing parameters, plus 10 minutes for the application of the ECG Belt and System set-up.

\*\*The DR220 Digital Recorder (NorthEast Monitoring, Inc, MA, USA) is a Holter monitor that is designed to facilitate the ambulatory cardiac monitoring and is intended for use with Medtronic System-B compatible implantable pulse generators, implantable cardiac defibrillators, and cardiac resynchronization therapy devices and implantable cardiac monitors. The Holter monitor will be used in accordance with its labeling. Only trained study personnel should apply the monitors. The data obtained by monitoring is not analyzed at the time of the recording. After the recording is complete, the data must later be returned and analyzed at Medtronic. **No personal information will be entered and collected by DR220 recorder.**

For the purposes of this study, the Holter will be used during the in-office monitoring and will be removed at the conclusion of the monitoring. Each patient will have one DR220 Holter monitors collected during the study.

The Holter Recorder has application for any subject with a Medtronic IPG. For the purposes of this study, the intended use of the Holter Recorder is to acutely uplink continuous EGM signals that will be collected by the IPG in Holter mode.

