## **4.2 Study Population**

### **4.2.1 Approximate Number of Subjects**

Approximately 20 patients will participate in the ECG Belt study to be conducted at Geisinger Heart Institute.

All patients will share the same recruitment process, inclusion and exclusion criteria and same procedures.

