#### **4.6 Primary Endpoints**

The primary endpoints will be

- ECG Belt analysis of Standard Deviation of Activation Times (SDAT) of LBBAP compared to native conduction
- ECG belt analysis of Left Ventricular activations times (LVAT) of LBBAP compared to baseline
- ECG belt analysis of SDAT and LVAT of HOT-CRT compared to baseline
- ECG belt analysis of QRS duration at baseline compared to various LBBAP options
- Comparison of above parameters of LBBP to historic biventricular or RV pacing

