#### **4.8 Statistics**

Summary tables of descriptive statistics will be provided for all variables. Continuous variables will be summarized using means and standard deviations or median and interquartile ranges (IQR), depending on distributional assumptions. Categorical variables will be summarized using percentage and frequency counts. The descriptive statistics will be reported for Baseline and follow-up (adverse events only will be collected).

Analysis of the following objectives will be accomplished using the Chi-square or Fisher's exact tests, and T-tests or non-parametric test (Median test, Wilcoxon rank sum test, etc.), as appropriate.

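### Section 4.5 yields several paced recordings per patient, but 4.6 and 4.8 do not say which recording feeds each endpoint or plan a within-patient analysis

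*Combined protocol and SAP*

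**What the plan says.** Section 4.5 (Visit 1 – Baseline) lists the Belt recordings in two sequences. The LBBP sequence includes native conduction, "Bipolar LBBAP", "Unipolar LBBAP – nonselective and selective (different outputs" and "Fusion pacing with native conduction at different AV delays". The HOT-CRT sequence includes native conduction, HBP or LBBAP, HOT-CRT, and "AV delay optimization". Section 4.1 also calls for both unipolar and bipolar LBBAP recordings.

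The first primary endpoint in 4.6 is "ECG Belt analysis of Standard Deviation of Activation Times (SDAT) of LBBAP compared to native conduction". The LVAT and HOT-CRT endpoints are worded in the same way, with no configuration, output or AV delay named. Only the QRS endpoint admits several paced states: "ECG belt analysis of QRS duration at baseline compared to various LBBAP options". It gives no rule for handling them.

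Section 4.8 plans "T-tests or non-parametric test (Median test, Wilcoxon rank sum test, etc.), as appropriate" and repeats the SDAT and LVAT comparisons. QRS duration is not in that list, although descriptive statistics are promised for every variable. No unit of analysis is stated, and no paired or repeated-measures method is named. Section 4.8 also says that the study is for gathering information, that test results are not conclusive, and that they will be used to design a larger study.

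On size, 4.2.1 says "Approximately 20 patients will participate in the ECG Belt study". Eligible systems in 4.2.2 are LBBAP, LBBAP plus an LV lead, or HBP plus an LV lead.

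**The concern.** Two things are missing, and they compound each other.

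- **The endpoint value is undefined.** A patient in the LBBP sequence can supply at least three LBBAP recordings (one bipolar, two unipolar), and five or more if fusion at two or more AV delays is counted. Nothing says which one is the patient's LBBAP value, whether recordings are averaged, or whether fusion counts as LBBAP. For HOT-CRT, nothing says what the AV delay is optimised on, or whether the recording used to choose it is also the endpoint.
- **The named tests ignore the pairing.** Native and paced recordings come from the same patient in the same session. The Median test and the Wilcoxon rank sum test assume independent groups, as does an unpaired t-test.

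At stake are the estimates more than the p-values. Section 4.8 hands these results to the design of a larger study, so a difference inflated by selection, or an SD computed on the wrong unit, would go into its sample size.

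**Working it through.** The documents give no alpha, SD, effect size or power calculation, so there is no planned figure to reproduce.

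**Input from the documents.** n = 20 (4.2.1); the split between LBBAP and HOT-CRT is not given.

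**Assumptions, not in the documents.** k = 3 or 4 paced recordings per patient; within-patient correlation ρ = 0.5 to 0.9; normal data; equal means and SDs (σ) for native and every paced recording, so there is no true effect; two-sided 5% level. Rejection rates were simulated (40,000 trials per setting; 200,000 for step 1).

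**1. One paced value against native, unpaired test.**
- True variance of the mean difference: 2σ²(1−ρ)/n. The unpaired test uses 2σ²/n.
- Ratio of standard errors: 1/√(1−ρ) = 1/√0.5 = 1.41 at ρ = 0.5, and 1/√0.1 = 3.16 at ρ = 0.9.
- True level at ρ = 0.5, normal approximation: 1.96 × 1.41 = 2.77, two-sided tail 0.56%. Simulation with the t-test at n = 20 gives 0.7%, falling to effectively 0 at ρ = 0.9.

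**2. All k paced-minus-native differences counted as independent.**
- Each difference has variance 2σ²(1−ρ). Two differences from one patient share the native reading, with covariance σ²(1−ρ), so their correlation is 0.5 whatever ρ is.
- Design effect at k = 4: 1 + 3 × 0.5 = 2.5. The standard error is too small by √2.5 = 1.58.
- True level: 2 × [1 − Φ(1.96/1.58)] = 21.5%; simulated, 22%.

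**3. Lowest of k readings against one native reading, paired t-test.**
- The expected minimum of three independent standard normals is −0.85. Scaled by √(1−ρ), the spurious shortening is 0.85 × 0.707 = 0.60 SD at ρ = 0.5 and 0.85 × 0.316 = 0.27 SD at ρ = 0.9.
- Simulated rejection rate at k = 3: 82%.

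**4. All paced recordings pooled against native, unpaired t-test.** Simulated level 0 to 0.8%. This pooling is conservative.

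**5. One value per patient (mean of the k recordings), paired t-test.** Simulated level 4.9 to 5.3%. A single configuration named in advance, tested with a paired t-test, has the nominal level by construction under these assumptions.

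The error can therefore go in either direction, depending on a choice that the plan leaves open. With the patient as the unit and a paired analysis, the nominal level returns.

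**The case against.** The strongest reply is that nothing here is planned wrongly. The natural reading of 4.1 and the QRS endpoint is one comparison per configuration, with one value per patient, which involves neither selection nor pooling. Averaging is equally open. The test list in 4.8 is open-ended and says that tests will be used as appropriate, so a paired t-test or signed-rank test is not excluded. The tests are expressly non-conclusive. The pacing configurations are also different states rather than replicates, so the lowest reading mixes real differences with noise, and the documents give no Belt reading error from which to size the noise in milliseconds.

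Much of this stands. A reader might infer that the analyst is forced either to pick the best reading or to pool them all; the documents force neither. A reader might infer that pooling always makes standard errors too small; step 4 shows the opposite for an unpaired comparison with native. Nor does every patient yield both LBBAP and HOT-CRT recordings: 4.2.2 admits LBBAP-only systems and HBP plus LV systems. Fusion is listed apart from bipolar and unipolar LBBAP, so its membership in LBBAP is unsettled. Section 4.5 does not say that the AV delay is tuned on SDAT or LVAT, or that the tuned recording is the endpoint.

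What the reply does not supply is a rule. An open list is no plan for repeated measurements when both rank-type tests it names are for independent samples. The exploratory status lowers the weight of the rejection rates, but it does not protect the difference and SD passed on to the next study.

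**Conclusion.** The point holds as a gap in the endpoint definition joined to named non-parametric tests that do not fit within-patient data. It does not hold as a charge that the plan builds in best-of-k selection or pseudo-replication.

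Under the stated assumptions, an unpaired standard error is 1.4 to 3.2 times too large, with a true level of 0 to 0.7%. Pooling four paired differences per patient gives about 22%, and the lowest of three readings gives about 82%, with a spurious shortening of 0.27 to 0.60 SD. The number of recordings and the correlation are assumed, and the selection figures also treat the configurations as equal in truth, so they illustrate direction and scale rather than predict this study's error. The change should be made, but the descriptive purpose and small size keep it below a critical fault.

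**What to change.** **In 4.8:** state that the patient is the unit of analysis. Analyse SDAT, LVAT and QRS duration with a mixed model (configuration as fixed effect, patient as random intercept), or with paired comparisons configuration by configuration. Report every configuration-minus-native difference with a 95% CI. Keep fusion as its own level, separate from LBBAP. Each patient contributes only the configurations that their system allows.

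**In 4.6:** before data are seen, name one reference LBBAP recording for the headline SDAT and LVAT contrasts, for example the bipolar one. This is a choice of measurement for analysis and has no bearing on how the device is programmed for care.

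**For HOT-CRT:** state what the AV delay is optimised on. If it is Belt SDAT or LVAT, take the endpoint from a repeat recording at the chosen delay in the same session, or label the optimised value as selected when reporting it.

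**Cost:** wording in two sections, slightly more analysis, and at most one short repeat recording for HOT-CRT patients. The headline effect may look smaller than a best-of-k value would.

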### **Monitoring (Scheduled Follow-up)**

Total period of 1 week (+/- 5 days) starting after baseline visit, during which the subject will be contacted by phone to assess any adverse events related to the ECG Belt. Patients will be followed in the device clinic as per standard of care.

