#### **4.4 Study Duration**

##### **4.4.1 Approximate Duration of Subject Participation**

Subjects will participate in the study for approximately 1 week (+/- 5 days). This includes a monitoring (follow up) period which starts immediately after signing the Informed Consent and completing the baseline visit (visit 1).

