##### **4.4.2 Approximate Duration of Study**

This study will be completed in approximately 12-15 months duration. The end of the ECG Belt study is the completion of data entry and statistical analysis.

This study duration approximation is composed of the following stages:

- Screening and Enrollment Stage – enrollment of 20 patients from Geisinger Heart Institute is expected to take 10-12 months based on enrollment rate of 1 to 2 subjects per month.
- Monitoring Stage – based on the planned 1 week monitoring period for each patient, last patient completed is expected 10-12 months from the study beginning.

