### **Study Exit**

Once the 1-week follow-up is completed, the subject is considered exited from the study, unless there is unresolved system related AEs with further actions or treatments planned.

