**CONFIDENTIAL AND PROPRIETARY**

- 
- a- Potential patients will be identified by clinician referrals. All patients will share same recruitment process and procedures
  - b- Only adverse event related to the use of the ECG Belt and/or device malfunctions
  - c- The use of the ECG Belt Research System might add approx. 40 minutes of time to f/u visits for testing parameters, plus 10 min for system set up.
  - d- When 1-week f/u is completed, subject is considered exited from the study unless unresolved system related AEs occur. An unscheduled follow-up visit may be required.
  - e- Special attention to: ACE/ARB, beta blockers, diuretics, and anti-arrhythmic use

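### The ±5-day window lets the only scheduled adverse-event call fall as early as day 2, leaving the rest of the planned week without active ascertainment (minor)

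*Combined protocol and SAP*

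**What the plan says.** The combined protocol and SAP describes the follow-up in several places.

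- **With the tolerance.** Section 4.4.1: "Subjects will participate in the study for approximately 1 week (+/- 5 days". Section 4.5, Monitoring: "Total period of 1 week (+/- 5 days) starting after baseline visit, during which the subject will be contacted by phone". The Schedule of Events (4.5.1) has one Week 1 phone column with a visit window of ±5 days, counted from Visit 1 on Day 0.
- **Without the tolerance.** The opening list of section 4.5: "1-week follow-up monitoring period for adverse events (phone call". The timeline in section 4.4.2: "based on the planned 1 week monitoring period for each patient".
- **Exit.** Section 4.5, Study Exit: "Once the 1-week follow-up is completed, the subject is considered exited from the study, unless there is unresolved system related AEs". Footnote d to the Schedule of Events repeats the rule and adds "An unscheduled follow-up visit may be required".
- **Use of the data.** Section 4.8 plans descriptive statistics for baseline and follow-up, and adverse events are the only data collected at follow-up. Sections 4.6 and 4.7 do not make them an endpoint.

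**The concern.** A tolerance of 5 days on a nominal 7 is wide, and its early side removes most of the period that the call is meant to cover. One phone call is the only scheduled contact, so its date decides how much of the week is actively asked about. Two patients handled equally correctly could be observed for very different lengths of time.

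At stake is the safety description of an investigational device. Section 5 expects skin redness, irritation and discomfort, notes that the affected area may be larger than with standard electrodes, and accepts that other risks may be unknown. For an unknown risk, one cannot presume that onset comes before day 2. A proportion of patients with a belt-related event, taken over unequal observation, would be hard to interpret and could miss later-onset events.

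**Working it through.** The plan gives no derived figure to reproduce, so the check is arithmetic on the window and a comparison of the sections.

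**Inputs.** Nominal length is 7 days and tolerance ±5 days (4.4.1, 4.5 Monitoring, Schedule of Events). About 20 patients (4.2.1). One scheduled contact after Visit 1 (4.5, Schedule of Events).

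**Step 1: permitted call days.** Earliest: 7 − 5 = day 2. Latest: 7 + 5 = day 12. That makes 12 − 2 + 1 = 11 permitted days and a 12/2 = 6-fold range. A day-2 call covers 2/7 = 29% of the nominal week.

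**Step 2: when exit occurs.** The Monitoring paragraph attaches the tolerance to the period; the Schedule of Events attaches it to the contact. Exit is tied to completion of the 1-week follow-up. There are two readings:

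- The period itself may be as short as 2 days, so exit can come on day 2.
- The call comes early and exit waits until day 7.

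Under either reading, no contact is scheduled between a day-2 call and day 7. The gap in active ascertainment does not depend on which reading is right.

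**Step 3: how much of the week might go unasked (illustration).** The documents say nothing about when calls will be made. Assume they are spread evenly over days 2 to 12:

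- Calls before day 7: 5/11 = 45%, or about 9 of 20 patients.
- Mean coverage of the first 7 days: (2 + 3 + 4 + 5 + 6 + 6 × 7)/11 = 62/11 = 5.64 days.
- Shortfall: 1 − 5.64/7 = 19.5% of 20 × 7 = 140 patient-days, about 27.
- Mean follow-up without truncating at day 7: 77/11 = 7.0 days, exactly the nominal week.

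If every call fell on day 2, the shortfall would be 1 − 2/7 = 71%. If none fell before day 7, it would be zero.

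**Step 4: what that could mean in events (illustration).** The documents give no onset data. Assume exponential onset with mean m days, F(t) = 1 − exp(−t/m). For a patient called on day 2, the share of 7-day events starting after the call is 1 − F(2)/F(7):

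| Mean onset m (days) | F(2) | F(7) | Share after day 2 |
|---|---|---|---|
| 0.5 | 0.982 | 1.000 | 1.8% |
| 1 | 0.865 | 0.999 | 13.5% |
| 2 | 0.632 | 0.970 | 34.8% |
| 4 | 0.393 | 0.826 | 52.4% |

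The range runs from negligible to about half, driven entirely by the assumed m. These figures apply to the earliest permitted call; later calls miss less.

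**The case against.** The best defence is that the tolerance is openly part of the stated period. Sections 4.4.1 and 4.5 and the Schedule of Events all show it, and sections 4.4.2 and the opening of 4.5 can fairly be read as shorthand. That stands: a reader might infer that the protocol contradicts itself or fails to deliver a promised week, but the documents show only that a full week is not guaranteed.

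A reader might also infer that the patient leaves the study at the call. Neither Study Exit nor footnote d says so; both refer to completion of the 1-week follow-up. Exit at the call is one possible reading.

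Nor do the documents support saying that events after an early call are lost. Other routes exist: 

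- the unscheduled visit, where adverse events are marked for collection;
- the patient's own physician (5.1);
- standard device-clinic care (4.5);
- chart review with dates (4.9.1);
- notification of serious incidents (5.2).

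These are passive, and none is stated to collect ordinary belt-related reactions systematically after the call. Later events are therefore unsolicited, not lost. The Visit 1 list in section 4.5 also includes belt-related adverse events, which should catch immediate reactions, although the Schedule of Events does not mark that row for Visit 1.

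Finally, the plan promises no one-week event rate, adverse events are not an endpoint, and section 4.8 disclaims hypothesis testing. This limits the consequence to the quality of a descriptive safety summary. It does not remove the point, because that summary is all the follow-up data the study will report.

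**Conclusion.** The point holds as a minor one. By the stated rule, the single scheduled adverse-event call may fall anywhere from day 2 to day 12. An early call leaves up to 5 of the 7 days without active ascertainment, and the timing of exit is unclear. The summary in section 4.8 would then combine observation periods that differ up to 6-fold and could miss later-onset belt-related events.

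The window arithmetic needs no assumption. The effect on reported events is unknown: the 19.5% and 71% shortfalls rest on assumed call dates, and the 1.8% to 52.4% range on assumed onset times. None of these is an estimate of bias. For skin reactions that appear during or soon after one non-invasive session of about 50 minutes, the effect is probably small. The case for changing the rule rests on the acknowledged unknown risks and on how little the change costs.

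**What to change.** In sections 4.4.1 and 4.5 and in the Schedule of Events:

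- make the Week 1 call window one-sided: day 7, −0/+5 days;
- state in Study Exit and footnote d that exit follows completion of that call, keeping the existing exception for unresolved system-related events;
- have the caller ask about the whole interval since Visit 1 and record the onset day of each event.

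Every completed call then covers at least 7 days. Observation would still run from 7 to 12 days, but the recorded onset days allow events in the first 7 days to be summarised on a common basis in section 4.8.

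The cost is a short wording change and a calling window of 6 days (7 to 12) instead of 11, with slightly more scheduling effort. Visits, endpoints and sample size are unaffected.

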### **Study Exit**

Once the 1-week follow-up is completed, the subject is considered exited from the study, unless there is unresolved system related AEs with further actions or treatments planned.

#### **4.5.1 Schedule of Events**

|  | Clinic                         | Phone       | Clinic                   |
|--|---------------------------------------|--------------------|---------------------------------|
| Visit                           | Visit 1 – Baselinea | Week 1 F/U  | Unscheduled d |
| Visit Window                    | Day 0                          | (+/-5 days) |                                 |
| Medical Records Review                 | X                              |                    |                                 |
| Informed Consent                       | X                              |                    |                                 |
| Inclusion/Exclusion                    | X                              |                    |                                 |
| Medical History                        | X                              |                    |                                 |
| Demographics                           | X                              |                    |                                 |
| Concomitant Medication e    | X                              |                    |                                 |
| NYHA Functional Classification         | X                              |                    |                                 |
| Device interrogation                   | X                              |                    |                                 |
| ECG Belt System procedure c | X                              |                    |                                 |
| ECG 12 Lead                            | X                              |                    |                                 |
| Adverse Events/ SAE b       |                                       | X           | X                        |

